### **Study Protocol**

Patients are divided into 2 groups based on randomization that occurs on the day of the first injection. Pre-procedural data categorization will be entered at the time of group assignment.

#### **Repeat Injection Criteria:**

An patient who achieves at least 80% relief immediately after the injection and subsequently reports less than moderate relief (<50% relief on NPRS) at any point in the study will be offered repeat sacroiliac joint steroid injection. Repeat injection will be performed on the same side(s) as the initial injection and with the same steroid the patient was initially randomized to. If any additional injections are deemed warranted by the treating physician the patient will be considered a treatment failure in the study.

**Injection:** Unilateral or bilateral Injection will be allowed at the discretion of the treating physician.

#### **Co-Intervention:**

Patients are allowed to receive usual care, including co-interventions, as deemed necessary by the treating physician.

#### **Primary Outcomes:**

The primary outcome is comparison of successful treatment rates between groups at 2-4 weeks as defined as moderate or good response to treatment (at least 50% improvement in index NPRS pain) at 2-4 weeks follow up. Other comparisons between groups based on NPRS outcomes include categorical comparison of:

1. Moderate or good response at 3 months
2. Number of injections needed to achieve moderate or good response at 3 months.

#### **Secondary Outcomes:**

1. Disability (ODI)

#### **Data Management**

Data will be collected on standardized case report forms and entered into a database on HIPPA-compliant encrypted Vanderbilt laptop (e.g. Microsoft Excel). All study-related hard copy materials will be stored in locked file cabinets.

### Analysis

Results of this randomized prospective pragmatic trial will be primarily determined by comparative analysis of comparative data at 4 weeks and 3 months. Overall success as defined by at least moderate response (at least 50% improvement on NPRS at 4 weeks and 3 months will be calculated for the entire cohort. No cross over will be allowed. Intention to treat analysis will be used. All adverse events will be recorded and reported.

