### **Specific Aims:**

1. Compare the proportion of patients between groups with a good response (80% or greater improvement in index pain) after sacroiliac joint corticosteroid injection at 2-4 weeks and 3 months.

2. Compare the proportion of patients between groups with a moderate response (50% or greater improvement in index pain) after sacroiliac joint corticosteroid injection at 2-4 weeks and 3 months.
3. Compare the proportion of patients between groups who have at least 30% improvement in ODI at 2-4 weeks and 3 months
4. Compare the proportion of patients between groups who have ODI score less than 20% at 2-4 weeks and 3 months.
5. Compare the proportion of patients between groups who had a good response at 2-4 weeks that continue to have good response at 3 months
6. Compare the proportion of patients between groups who had a good response at 2-4 weeks that continue to have at least moderate response at 3 months.
7. Compare the number of patients who have at least moderate response at 2-4 weeks who require repeat injection prior to 3 months.
8. Compare the number of patients with cessation of pain medication use, other than over-the-counter medication, for index pain at 2-4 weeks and 3 months
9. Report Adverse Events

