## Power Analysis

A total of 102 patients (51 dexamethasone and 51 methylprednisolone) will provide over 80% power to detect a difference of 20% between groups in the proportion of patients achieving at least moderate improvement on the NPRS using repeated measures binary logistic regression with a level of significance of  $\alpha = 0.05$ . This calculation is based on previous literature showing the proportion of patients achieving at least moderate improvement to be roughly 50% (1). Additionally, this calculation conservatively assumes moderate autocorrelation among the time points and includes an extra 15% to account for potential loss to follow up.

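### The named primary test uses one visit while the hypothesis and Analysis section rest on two, with no combining rule, and five of the aims have no stated status

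*Combined protocol and SAP*

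**What the plan says.** Four sections bear on what decides the trial.

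- **Primary Outcomes:** "The primary outcome is comparison of successful treatment rates between groups at 2-4 weeks", with success meaning at least 50% NPRS improvement. Response at 3 months and the number of injections needed are listed beneath it as other comparisons.
- **Hypothesis:** the null concerns the same 50% NPRS response, but at 4 weeks and 3 months.
- **Power Analysis:** the trial is sized "to detect a difference of 20% between groups in the proportion of patients achieving at least moderate improvement on the NPRS", using repeated-measures binary logistic regression at a level of 0.05.
- **Analysis:** "Results of this randomized prospective pragmatic trial will be primarily determined by comparative analysis of comparative data at 4 weeks and 3 months".

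Specific Aims lists eight between-arm comparisons, five of them at two visits, plus adverse-event reporting. The first aim begins "Compare the proportion of patients between groups with a good response (80% or greater improvement in index pain". Secondary Outcomes has a single entry, disability on the ODI. No section gives a multiplicity adjustment, a testing order or an exploratory label. Data Analysis names tests only for baseline differences.

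**The concern.** The sections agree on the endpoint but not on the time point. One visit decides under Primary Outcomes. Both visits decide under the Hypothesis and Analysis sections, and the plan does not say whether a difference is needed at either visit, at both, or in one test across them. Each rule has a different error rate and a different power, and the choice could be made after the data are seen.

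The aims add a second problem. The Secondary Outcomes entry covers Aims 3 and 4, and Primary Outcomes covers Aim 2. Aims 1, 5, 6, 7 and 8 are classified nowhere. The trial asks whether dexamethasone works as well as a particulate steroid. If the named comparison shows no difference, one chance p-value on the 80% cut-off, on an ODI cut-off or on durability could be presented as one steroid being better, and nothing in the plan would mark that result as supportive only.

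**Working it through.** **1. The plan's own figure.** Inputs from the Power Analysis: 51 per arm, a 20-point difference, a reference rate near 50%, level 0.05, and 15% extra for loss. Evaluable per arm is 51 × 0.85 = 43.4 or 51/1.15 = 44.3, so 43-44. The correlation between visits is called moderate with no value, and sidedness is not stated.

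Power for 50% vs 70% (30% vs 50% gives the same), with n per arm, two-sided:

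Φ[(0.20 − 1.96·√(2·0.6·0.4/n)) / √((0.25 + 0.21)/n)]

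For a test using both visits, n is replaced by 2n/(1+ρ), which assumes the same effect at each visit.

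| Test, two-sided | n = 43 | n = 44 | n = 51 |
|---|---|---|---|
| Early visit only | 47% | 48% | 54% |
| Both visits, ρ = 0 | 77% | 78% | 84% |
| Both visits, ρ = 0.3 | 65% | 66% | 73% |
| Both visits, ρ = 0.5 | 59% | 60% | 67% |

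The stated power of over 80% is not reproduced two-sided after loss. One-sided, with 44 per arm, it is just reached at ρ = 0.2 (80.1%). An early-visit test alone would need 93 per arm for 80%.

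**2. Error rate of the main conclusion.** Two tests of the 50% NPRS response, each two-sided at 0.05, with no true difference. With independent visits, P(either) = 1 − 0.95² = 9.75%. With correlated visits, P(either) comes from the bivariate normal distribution, and P(both) = 0.05 + 0.05 − P(either).

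| Assumed correlation | Either visit | Both visits required |
|---|---|---|
| 0 | 9.75% | 0.25% |
| 0.3 | 9.5% | 0.5% |
| 0.5 | 9.1% | 0.9% |
| 0.7 | 8.3% | 1.7% |

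A single pre-named test, at one visit or jointly across both, has 5%. Simulation with Pearson tests at these sample sizes gave about 8-12% for the either-visit rule. Values above 9.75% reflect the discreteness of the test.

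**3. Count of comparisons.** Aims 1-4 at two visits, 8. Aims 5, 6 and 7, 3. Aim 8 at two visits, 2. Number of injections from Primary Outcomes, 1. Total 14; the primary and the 3-month response are the two Aim 2 comparisons and are not counted again. With one repeated-measures test for each two-visit endpoint, the count is 5 + 3 + 1 = 9.

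**4. Chance of at least one p<0.05 across the set, no true difference.** Under independence, 1 − 0.95¹⁴ = 51.2% and 1 − 0.95⁹ = 37.0%. The comparisons are correlated, so the 14 were also simulated: 4,000 null trials per setting, 43 and 51 per arm. Assumed rates were 50% and 30% for the two NPRS cut-offs, 45% and 35% for the two ODI cut-offs, and 30% for stopping medication. Repeat injection was modelled from early and late response.

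| Assumed correlation | Pearson | Pearson, Fisher for small cells | Fisher throughout |
|---|---|---|---|
| 0.5 to 0.7 | 42-46% | 39-44% | 28-31% |
| 0.8 | 37-40% | 35-37% | 24-27% |

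Over all settings, including weaker correlation, the range was about 24-49%.

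**The case against.** The strongest answer is that the plan does name one primary outcome at one visit and calls the NPRS items beneath it other comparisons. If that section governs, the error rate of the primary conclusion is 5%, whatever else is reported. The Hypothesis, Power Analysis, Primary Outcomes and Analysis sections also share the 50% NPRS endpoint, and none of them promotes the 80% response, ODI, durability or medication aims. Being listed first does not make Aim 1 the lead result. All of this stands.

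A reader might infer more: that any of the 14 comparisons may decide the trial, so that a chance of a false finding near one half is built in. The documents do not support that. No section gives the 14 equal standing. A planned comparison is not necessarily a test at 0.05, since outcome tests are not specified beyond the model in the Power Analysis. The documents give no correlations, and no response rates for the other aims, from which to derive one figure. The count itself falls to nine if that model is applied to each two-visit endpoint.

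The objection does not remove the contradiction over visits. The Hypothesis and Analysis sections state that both visits determine the result, and the Power Analysis sizes a model that is not the single-visit comparison in Primary Outcomes. Nor does it give Aims 1, 5, 6, 7 and 8 a status.

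**Conclusion.** The concern holds as a contradiction in the stated decision rule, together with an unranked set of aims. If a difference at either visit counts, the false-positive rate for the main conclusion is about 8-10% instead of 5%. This assumes two-sided tests at 0.05 and a correlation between visits of 0 to 0.7. The documents do not state the either-visit rule; they leave it open. Requiring both visits would instead bring the rate below 2%.

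Across all comparisons, the chance of at least one p<0.05 is 51% (14 tests) or 37% (nine tests) under independence, and roughly 25-50% for the 14 under assumed correlations, rates and test types. This describes the whole set. It is not the error rate of the named primary test, which is 5%.

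**What to change.** Reconcile the Hypothesis, Power Analysis, Primary Outcomes and Analysis sections so that one pre-named test of the at-least-50% NPRS response alone decides the trial at 0.05, with sidedness stated.

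- As Primary Outcomes now reads, this is the 2-4 week comparison. It can be taken as the early-visit contrast from the repeated-measures model, which keeps the planned method.
- If the sponsor intends both visits to count, use one joint test across them, or split alpha. At 0.025 per visit the either-visit rate is at most 1 − 0.975² = 4.9% for independent visits, and cannot exceed 5%.

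In Primary Outcomes and Secondary Outcomes, label every other comparison from those sections and Specific Aims as secondary or exploratory. Report these as estimates by arm with 95% confidence intervals, not as confirmatory findings.

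The change is to wording only; it adds no visits or data. It has two costs. The sponsor gives up confirmatory claims on the other aims; the Power Analysis claims power only for the 50% NPRS response. The choice also exposes the power: if the early visit alone decides, two-sided power for 50% vs 70% is about 47-48% at 43-44 per arm (54% at 51). A joint test does better, at 59-66% with 43-44 per arm and an assumed correlation of 0.5 to 0.3, but still misses 80%. The Power Analysis statement must be redone for the test chosen, with the correlation given as a number.
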